Understanding that environmental factors can potently and sometimes rapidly, favorably or negatively influence epigenetic expression, a short-term diet and lifestyle intervention may significantly augment DNA methylation expression.

The purpose of this study is to evaluate a 9-week diet and lifestyle intervention on patient-reported quality of life, symptoms, and DNA and biochemical methylation-related biomarkers in healthy males ages 50-72.

B. SPECIFIC AIMS

B.1 Primary Aim:

To evaluate a 9-week diet and lifestyle intervention on patient-reported quality of life.

Hypothesis: Quality of life will improve as a result a 9-week diet and lifestyle intervention, relative to a wait-list control condition.

Outcome measure: Changes in patient-reported quality of life, measured by the PROMIS-29 (Patient-Reported Outcomes Measurement Information System-29) questionnaire.

B.2 Secondary Aim:

To evaluate changes in patient-reported symptoms after a 9-week diet and lifestyle intervention.

Hypothesis: Severity of patient-reported symptoms will decrease following a 9-week diet and lifestyle intervention.

Outcome measures: Changes in patient-reported symptoms, measured by the MYMOP (Measure Yourself Medical Outcome Profile) questionnaire, NUNM Multi-system side effects/symptoms questionnaire, and the Medical Symptom Questionnaire (MSQ).

Protocol

Study Title: Methylation Diet and Lifestyle (MDL) Study

PI: [name], ND, MPH and [name], ND

IRB #: RB100217

Approval Date: 2.9.18

Ver. 1.1

B.3 Tertiary Aim:

To assess changes in methylation at CpG sites of DNA after a 9-week diet and lifestyle intervention.

Hypothesis: Methylation at CpG sites associated with chronic inflammation will change after the 9-week diet and lifestyle intervention.

Outcome measure: Number of CpG methylation sites, measured by the Infinium MethylationEPIC Kit (Illumina, Inc.)

B.4 Exploratory Aims:

To evaluate changes in biomarkers associated with methylation.

Outcome measures: Changes in the methylation related biomarkers as measured by Doctor's Data Methylation Index Panel, Methylation Profile, and Folate Vitamer Panel.

C. BACKGROUND AND SIGNIFICANCE

C.1. Methylation background and significance

Methylation, happening in every cell, virtually continuously, signifies the enzymatic addition of a single carbon compound on a substrate and regulates gene expression, protein function, and RNA processing.⁹ Folate vitamer, 5-methyltetrahydrofolate (5-MTHF) acts as key substrate within these pathways by transferring a methyl group to cobalamin by the enzyme methylenetetrahydrofolate reductase (MTHFR). This new compound, methylcobalamin, is a coenzyme used by methionine synthase and transfers a methyl group to homocysteine, creating methionine. Methionine undergoes a structural transformation under the presence adenosine triphosphate (ATP) to become S-adenosyl methionine (SAME). SAME, the universal methyl donor, is essential for over a 100 methylation reactions by transferring a methyl group to DNA, proteins, phospholipids, amino acids and neurotransmitters.

Research into the epigenome demonstrates that DNA methylation is a cornerstone regulator of gene expression. Genetic methylation is reliant on SAME availability. Myriad environmental factors, as outlined above, also influence genetic methylation either directly or through altered SAME availability.

Imbalances in methylation pathways due to single nucleotide polymorphisms (SNPs) is a rapidly emerging area of investigation implicated in numerous disease processes.¹⁰ While genetic polymorphisms alter enzyme function, it may increase risk of certain diseases.¹⁰⁻¹² Investigation into a single nucleotide polymorphism of MTHFR has gained popularity. Individuals with a point

Protocol

Study Title: Methylation Diet and Lifestyle (MDL) Study

PI: [name], ND, MPH and [name], ND

IRB #: RB100217

Approval Date: 2.9.18

Ver. 1.1

mutation on MTHFR gene, result in higher plasma levels of homocysteine, a risk factor associated with atherosclerosis and coronary artery diseases.^{13,14} Hyperhomocysteinemia is significantly inversely correlated with DNA hypomethylation and exacerbated by folate deficiency.¹⁵

C.2. Diet and lifestyle intervention as a means to support proper methylation

Inadequate diet and physical inactivity are indicated as two of the top 5 modifiable risk factors in several chronic diseases as well as associated with all-cause mortality.¹⁶ A diet lacking adequate intake of essential nutrients and antioxidants, as well as lack of exercise increase biomarkers associated with oxidative stress, endothelial dysfunction, and DNA hypomethylation.^{17,18} Oxidative overload places stress on cellular metabolic function, and is correlated with an increased risk of chronic diseases, such as cancer, cardiovascular and neurodegenerative diseases.¹⁹⁻²¹

With regard to the epigenome, poor diet has been associated with accelerated aging as evidenced by Horvath's Epigenetic Clock looking at DNA methylation patterns.⁸ Oxidative stress has also been shown to limit methyl donor availability, thereby impacting DNA methylation, by promoting transsulfuration and glutathione synthesis while inhibiting the methylation cycle. Oxidative damage to the epigenome further contributes to aberrant DNA methylation patterns.²²

A nutrient-rich diet and regular, moderate, aerobic exercise reduces oxidative stress, and risk of disease, by increasing antioxidants and activity of antioxidant enzymes, while also altering gene specific DNA methylation levels.^{7,23,24} Phytochemicals in various plant foods have demonstrated the ability to modulate DNA methylation. These include quercetin, found in red onion and apple skins, green tea, and red grapes; epigallocatechin-3-O-gallate (EGCG), found highest in green and white tea; genistein, found in soybeans; apigenin, found in parsley, artichoke, and celery; and curcumin, found in turmeric.²⁵ In addition, regular physical activity has shown to induce epigenetic changes in DNA methylation and lower homocysteine levels.^{26,27}

To date, this would be the first known clinical trial investigating diet and lifestyle intervention on patient-reported quality of life, symptoms, and DNA and biochemical methylation-related biomarkers in healthy males ages 50-72.

D. RESEARCH DESIGN AND METHODS STUDY FLOW

Protocol

Study Title: Methylation Diet and Lifestyle (MDL) Study

PI: [name], ND, MPH and [name], ND

IRB #: RB100217

[figure not shown]
Approval Date: 2.9.18

Ver. 1.1

D.1. Overview and Design

This study is a preliminary randomized control trial evaluating a 9-week diet and lifestyle intervention on quality of life, patient-reported symptoms, and biomarkers associated with methylation. We will recruit forty-eight participants with 24 randomized to each study group. Refer to Figure 1 for an overview of the study flow.

Figure 1. Study Flow Overview

D.2 Study Intervention

Study participants will be randomized into an intervention or control group. The intervention group will undergo a 3-week washout period following the discontinuation of any non-medically required nutrition or herbal supplements. The intervention group will follow detailed diet and lifestyle recommendations over a 9-week period. Two webinars at the start of the

Protocol

Study Title: Methylation Diet and Lifestyle (MDL) Study

PI: [name], ND, MPH and [name], ND

IRB #: RB100217

Approval Date: 2.9.18

Ver. 1.1

intervention phase will provide information to participants on proper food and exercise choices, as well as how to access and use the required electronic resources (apps).

The control group will undergo the same testing measures as the intervention group, but will not have access to the education information or be instructed to change diet or lifestyle factors. They will have access to the information after the study is complete.

D.2.1 Diet Recommendations

Specific dietary guidelines will be outlined for participants and should include the following:

Per week	Per day

3 servings of liver
 
 • (1 serving = 3 oz) • Choose preferably organic liver 
5-10 eggs
 
 • Ideally free-range, organic, omega-3 enriched 	
2 cups of dark leafy greens
 
 • Measured raw, chopped, and packed • Including kale, Swiss chard, collards, spinach, dandelion, mustard greens • Does not include salad greens such as romaine, iceberg, Spring mix 
2 cups cruciferous vegetables
 
 • Measured raw, chopped, and packed • Including broccoli, cabbage, cauliflower, Brussels sprouts, bok choy, arugula, kale, watercress, rutabaga, kohlrabi, radish, turnip
General	

Choose organic at least half of the time.
 
Stay hydrated
 
Don't eat between 7pm and 7am, and at least 2 hours before bed
 
Include healthy oils
 
 • Balance types of fat • E.g. coconut, olive, flaxseed and pumpkin seed oil 
Avoid dairy, grains, legumes/beans
 
Minimize plastic food containers
	
3 cups colorful, low glycemic vegetables of your choosing
 
1-2 medium beet
 
4 tbsp (1/4 cup) pumpkin seeds (or pumpkin seed butter)
 
4 tbsp (1/4 cup) sunflower seeds (or sunflower seed butter)
 
1+ serving methylation adaptogens:
 
 • 1/2 cup berries (wild preferred) • 1/2 tsp rosemary • 1/2 tsp turmeric • 2 medium cloves garlic • 2 cups green tea (brewed 10 minutes) • 3 cups oolong tea (brewed 10 minutes) 
6 oz animal protein
 
 • grass-fed, pastured, organic and hormone/antibiotic-free 
2 servings of low glycemic fruit

These recommendations serve as a guidance, while individual intake may vary based on preference. Throughout the study, participants will be provided 2-week menu plans with recipes for all meals, snacks, smoothies.

Protocol

Study Title: Methylation Diet and Lifestyle (MDL) Study

PI: [name], ND, MPH and [name], ND

IRB #: RB100217

Approval Date: 2.9.18

Ver. 1.1

Refer to Appendix A for detailed nutrition recommendations.

D.2.2 Exercise Recommendations

Participants will be encouraged to exercise a minimum of 30 minutes at least 5 days per week at an intensity of 60-80% of maximum perceived exertion. Possible types of physical activity include, but not limited to, brisk walking, light jogging, hiking, dancing, yardwork, bicycling, and swimming.

D.2.3 Stress Management Recommendations

Participants will utilize the Cleveland Clinic's Stress Free Now application to engage in a variety of guided stress reduction techniques, including meditation and mindful breathing. Recommended frequency is twice daily, preferably morning and evening.

D.2.4. Lifestyle Recommendations

Participants are encouraged to average a minimum of 7 hours of sleep per night.

D.2.5. Study Supplements

Participants will be provided with two supplements. Details on the products are outlined in section D.12 of the protocol. Participants will take 2 servings of PhytoGanix and 2 capsules of UltraFlora Intensive Care probiotic daily, in divided doses.

D.2.6. Control group

The control group will be waitlisted during the study intervention phase. They will be provided with a copy of the intervention webinars and educational handouts after the study is concluded.

D.2.7. Tools to measure study variables and assist with adherence:

D.2.7.1. Mbody360 app

MBODY360 is a HIPAA-Compliant Web-based complete health & wellness coaching platform that connects practitioners to their patients and clients in real-time and tracks patient's engagement & compliance. It includes secure video, text chatting, and group coaching tools. Participants will track their sleep, supplement usage, exercise, stress management. Participant progress will be monitored daily by health coaches using the Mbody 360 app.

Participants will be prompted to answer the following questions each day:

- Did you eat according to program guidance?
- What did you eat that was not according to the program?

Protocol

Study Title: Methylation Diet and Lifestyle (MDL) Study

PI: [name], ND, MPH and [name], ND

IRB #: RB100217

Approval Date: 2.9.18

Ver. 1.1

- Did you complete at least 30 minutes of moderate intensity physical activity today?
- Did you complete the stress management program today? For how long?
- How many hours of sleep did you get last night?
- Did you take any new medications, prescription or over-the-counter, today?
 - *If yes, which new medication did you take?
- Did you take your study probiotic supplement today?
- Did you take your Phytoganix supplement today?

D.2.7.2. VioScreen

VioScreen is a validated food frequency questionnaire software program, which tracks food intake over the past 90 days. It will take approximately 20 minutes for participants to input their dietary information. Developed by the Nutrition Coordinating Center at the University of Minnesota, it utilizes a standardized food and nutrient database. All participants will complete this at Visits 1, 2 and 3.

D.2.7.3. Stress Free Now

Stress Free Now by the Cleveland Clinic is an application that seven different relaxation techniques, including mindfulness and meditation. Each technique lasts approximately 10 minutes.

D.2.7.4. Zoom

A web-based communication program, Zoom will be utilized for group webinars and Q&A sessions throughout the study.

D.2.7.5. Study Specific Food Frequency Questionnaire

Not all foods recommended and consumed during the study intervention may be captured by VioScreen. An additional food frequency questionnaire (FFQ), with approximately 250 foods and beverages, was created to assess consumption. It has been designed to be consistent with the validated block Brief FFQ by NutritionQuest. This will be administered electronically via RedCap online database to all study participants at Visits 1, 2, and 3.

D.2.7.5. Adherence phone calls

Participants will be contacted via phone once per week during the first 4 weeks of the study and every other week for the remainder of the study. Designated health coaches will assess for adherence to the study intervention including dietary, stress management, and exercise recommendations. Participants will be able to ask questions pertaining to the study intervention.

Refer to Appendix B for detailed script of these phone calls.

Protocol

Study Title: Methylation Diet and Lifestyle (MDL) Study

PI: [name], ND, MPH and [name], ND

IRB #: RB100217

Approval Date: 2.9.18

Ver. 1.1

D.3 Description of Participant Population

D.3.1. Participant Characteristics

Sample size: n=48

We will enroll and randomize up to 48 people which will allow for 20% attrition such that we have an evaluated sample size of 40 to allow for withdraws or dropouts.

Age: 50-72

Gender: Males only

Minorities: all racial and ethnic backgrounds will be recruited from the general population without preference or discrimination.

Vulnerable Populations (e.g. children, pregnant women, cognitively impaired): No vulnerable populations will be enrolled.

D.3.2. Inclusion and Exclusion Criteria

Individuals must meet the following participation criteria:

Inclusion criteria:

- Males, ages 50-72
- Willing to adhere to 9 weeks of a dietary and lifestyle program including specific nutrition and exercise guidelines
- Willing to avoid any over-the-counter medications, supplements or herbal products for the length of the study, except short-term use (<1 week) use at least 1 week before scheduled study visits
- Willing to have blood drawn three times and abstain from food or beverage intake for 10-12 hours before blood draws
- Willing to provide saliva samples
- Willing to track food intake, sleep, stress management techniques, and exercise daily
- Willing to drink a nutrient-enriched beverage and take a encapsulated probiotic daily
- Willing and able to use electronic devices and connect to the internet
- Able to speak, read and understand English

Exclusion criteria:

- Currently taking any of the following prescription medications
 - Proton pump inhibitors: omeprazole (Prilosec, Prilosec OTC); aspirin and omeprazole (Yosprala); lansoprazole (Prevacid, Prevacid IV, Prevacid 24-Hour); dexlansoprazole (Dexilent, Dexilent Solutab); rabeprazole (Aciphex, Aciphex Sprinkle); pantoprazole (Protonix)

Protocol

Study Title: Methylation Diet and Lifestyle (MDL) Study

PI: [name], ND, MPH and [name], ND

IRB #: RB100217

Approval Date: 2.9.18

Ver. 1.1

- H2-blockers: nizatidine (Axid, Axid AR, Axid Pulvules); famotidine (Pepcid, Pepcid AC); cimetidine (Tagamet, Tagamet HB); ranitidine (Zantac)
- These classes of medications are excluded due to direct (due to nutrient requirements for metabolism) and indirect (through impaired digestion and assimilation of nutrients).
- Use of nutrition supplements or herbal products not prescribed by a licensed healthcare provider for a medical condition
- Currently following a prescribed dietary/lifestyle program or initiate within the 30 days prior to baseline
- Initiation of or changes to an exercise regimen within 30 days prior to baseline
- Use of nicotine, marijuana or cannabinoids (including CBD products) or recreational drugs/substances (such as but not limited to cocaine, phencyclidine [PCP], and methamphetamine) current/within the last 30 days or use during the study
- Have a diagnosis of cardiovascular disease, kidney disease, liver disease, diabetes, autoimmune disease, high blood pressure, or cancer (does not include *basal cell carcinoma, squamous cell carcinoma, and/or carcinoma in situ of the cervix*).
- Have a diagnosis of an immunodeficiency condition, such as Human Immunodeficiency Virus (HIV) infection or Acquired Immune Deficiency Syndrome (AIDS)
- Have a diagnosis of neurodegenerative conditions such as, amyotrophic lateral sclerosis (ALS), Parkinson’s disease, Multiple Sclerosis, or Alzheimer’s disease.
- Excessive alcohol consumption (more than 4 drinks per day or 14 per week on average)
- Known sensitivity, intolerance or allergy to ingredients in the study supplements or in the recommended dietary therapy
- Currently receiving intravenous nutrient therapy
- Currently participating in another interventional research study or participated in another interventional study within the last 3 weeks prior to baseline

D.4 Outcome Measures

Table 1 below provides a summary of study outcomes, associated measures, and a brief description. More detailed descriptions of each measure are provided below Table 1.

Table 1.		
OUTCOME	MEASURE	DESCRIPTION
Primary Outcome		
Health-related Quality of Life	Patient Reported Outcomes Measurement Information (PROMIS-29)	PROMIS-29 is a validated, 29 question survey divided into seven sub-domains of function including physical functioning, social function, pain interference, pain intensity, sleep, depression, and anxiety.

Protocol

Study Title: Methylation Diet and Lifestyle (MDL) Study

PI: [name], ND, MPH and [name], ND

IRB #: RB100217

Approval Date: 2.9.18

Ver. 1.1

Secondary Outcome		
Change(s) in patient-reported symptoms	Measure Yourself Medical Outcome Profile (MYMOP)	MYMOP is a patient-centered outcome measure that allows for the participant to self-select their top health concern(s) or symptom(s) they are dealing with in their own words. The participant can also choose an activity that is limited by that health concern.
	NUNM Multi-system AE questionnaire	The NUNM Multi-system Symptom/Adverse Event Questionnaire is a standardized ninety-one point monitoring form that requires asking questions pertaining to the following organ systems: eyes/ears/nose/throat, gastrointestinal, neurological/musculoskeletal, psychological/general, cardiopulmonary, skin, genitourinary and whole body systems.
Tertiary Outcome		
Methylation status of CpG sites	Infinium Methylation EPIC Index by Illumina	Epigenetic profile that assesses methylation on over 850,000 CpG DNA sites
Exploratory Outcomes		
Changes in the methylation related biomarkers	Methylation Profile by Doctor's Data	Functional assessment of the phenotypic expression of common SNPs and provides a "methylation index," a ratio of SAM to SAH.
	Folate Vitamer Panel by Doctor's Data	Measures folate congeners affecting enzyme function in methylation pathways including unmodified Folic Acid (UMFA), 5-Methyltetrahydrofolate (5-MTHF), tetrahydrofolate (THF), folinic Acid (5-CHO-THF)
Change(s) in patient-reported symptoms	Medical Symptoms Questionnaire (MSQ)	The MSQ is a 71-question measure that measures various health areas including: Digestive tract, Eyes, Energy/Activity, Emotions, Head, Heart, Joint/Muscles,

Protocol

Study Title: Methylation Diet and Lifestyle (MDL) Study

PI: [name], ND, MPH and [name], ND

IRB #: RB100217

Approval Date: 2.9.18

Ver. 1.1

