- The Principal/Clinical Investigator decided that withdrawal/discontinuation was in the best interest of the participant due to an adverse event, non-compliance, or another reason
- The participant requests withdrawal from the study for reasons other than above
- The participant failed to return for study visits

If a participant withdraws before the second visit, they will be replaced, however participants who withdraw between the second and third visits will not be replaced. Every effort will be made to collect a final salivary sample and all final labs from all participants, even if they withdraw from the study early.

D.7. Study Products

D.7.1. PhytoGanix (tropical fruit flavor)

Organic Superfruits & Greens Powder Drink Mix is a food-based phytonutrient blend designed to support intestinal health and immune function.

Protocol

Study Title: Methylation Diet and Lifestyle (MDL) Study

PI: [name], ND, MPH and [name], ND

IRB #: RB100217

Approval Date: 2.9.18

Ver. 1.1

Serving Size: 1 Scoop (10.4 grams)

Ingredient	Amount per serving
Calories	40
Total Carbohydrate	9 g
Dietary Fiber	1 g
Sugars	1 g
Protein	1 g
Vitamin C (as ascorbic acid)	100 mg
Calcium	20 mg
Iron	1.4 mg
Sodium	30 mg
Organic Seed and Prebiotic Blend:	5.53 g
Isomalto-Oligosaccharide, Flax Seed Powder, Chia Seed Powder, Quinoa (Chenopodium quinoa Willd.) Sprout Powder	
Organic Veggie Blend:	2.35 g
Spirulina Whole Algae Powder, Carrot Root Powder, Broccoli Head Powder, Cauliflower Head Powder, Spinach Leaf Powder, Parsley Leaf Powder, Bamboo Shoot Extract, Beet Root Powder	
Organic Fruit Blend:	1.2 g
Apple Fruit Powder, Pineapple Fruit Powder, Strawberry Fruit Powder, Raspberry Fruit Powder, Blackberry Fruit Powder, Blueberry Fruit Powder	
Herbal Support Blend:	300 mg
Milk Thistle Seed Extract, Turmeric Rhizome Extract, Green Tea Leaf Extract, Reishi Mushroom Whole Plant Powder, Maitake Mushroom Whole Plant Powder, Shiitake Mushroom Whole Plant Powder, Japanese Knotweed Root Extract, Quercetin Dihydrate, Organic Maca Root Powder, Organic Cassia Bark Powder, Dong Quai Root Powder, Ginger Root Powder, Garlic Bulb Powder	
Enzyme Blend (including protease, amylase, lipase, and cellulase)	200 mg
Lactobacillus acidophilus VK3 Strain	200 mg

Protocol

Study Title: Methylation Diet and Lifestyle (MDL) Study

PI: [name], ND, MPH and [name], ND

IRB #: RB100217

Approval Date: 2.9.18

Ver. 1.1

D.7.2. UltraFlora Intensive Care

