Serious Adverse Event (SAE): Any untoward medical occurrence that results in death, is life-threatening, requires inpatient hospitalization or prolongation of existing hospitalization, results in persistent or significant disability or incapacity, or results in a congenital anomaly or birth defect. Other important medical events requiring medical or surgical intervention to prevent a serious outcome would also be considered SAEs.

Unanticipated Problems (UP): Any incident, experience, or outcome that meets all of the following criteria: 1) unexpected (in terms of nature, severity, or frequency) given (a) the research procedures that are described in the protocol-related documents, such as the IRB-approved research protocol and informed consent document; and (b) the characteristics of the subject population being studied; 2) related or possibly related to participation in the research and 3) suggests that the research places subjects or others at a greater risk of harm (including physical, psychological, economic, or social harm) than was previously known or recognized.

G.4. Statistical Analysis

PROMIS 29 T-scores will be presented as mean (SD), for each group at each of the three data collection time points. For the primary aim, we will compare changes in PROMIS-29 T-scores between groups, using a linear mixed model with random intercept to test for a Group*Visit interaction. If there is a significant main effect, we will also present uncorrected contrasts comparing changes from baseline to Week 5, and from baseline to Week 9, between groups.

Although PROMIS T-scores are not particularly susceptible to extreme outliers, data will be examined for any outlying PROMIS scores or changes in PROMIS scores. If these scores are deemed to be in error, then they will be treated as missing in all analyses. Otherwise, scores

Protocol

Study Title: Methylation Diet and Lifestyle (MDL) Study

PI: [name], ND, MPH and [name], ND

IRB #: RB100217

Approval Date: 2.9.18

Ver. 1.1

will be retained in the main analysis; but we will conduct separate sensitivity analyses to test for effects of outlying data on results.

Mixed models incorporate all available data, without excluding any participants from analysis. Nevertheless, any participants who have baseline data only will be excluded from analysis. As an exploratory follow-up analysis, we will re-analyze changes from Week 1 to Week 9, using data from completers only.

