For the secondary aim, the total score of the MSQ will be analyzed similarly to PROMIS-29. Since MYMOP asks for two symptoms without distinction, we will classify each problem as either the *Primary* problem (the problem with the highest symptom rating at baseline; or, in the case of a tie, the first problem listed) or the *Secondary* problem. We will also calculate the *average* of the two problem scores, at each collection time point. If only one problem is listed, then this will be used as both the Primary and Average, for that individual, with Secondary score missing. Changes in MYMOP severity scores will be compared between groups using a non-parametric Mann-Whitney test. Separate comparisons will be made between changes over the first 4 weeks of the study and changes over the entire 9-week intervention period.

G.5 SPONSOR RESPONSIBILITIES FOR INTERVENTIONAL PRODUCT(S)

The sponsor, Metagenics, is responsible for supplying the interventional product(s) in accordance with Good Manufacturing Practices (GMP). These products will be fully characterized, properly coded and suitably packaged in a way to provide protection against deterioration with appropriate labelling. Sufficient samples of each batch and a record of analyses and characteristics will be kept by the sponsor for reference so that, if necessary, an independent laboratory is able to re-check the interventional product(s), e.g. for quality control or bioequivalence. Records of the quantities of interventional products supplied will be maintained with batch or serial numbers by sponsor. The sponsor will ensure that the investigator is able to establish a system within their institution for adequate and safe handling, storage, use during the course of the study and, if appropriate, return or destruction of the interventional product(s) upon completion of the study.

G.6 SPONSOR MONITORING

The sponsor, Metagenics, will appoint suitable and appropriately trained monitor(s) and clinical research support personnel to conduct regular site visits starting with recruitment and continuing on a schedule that is mutually agreed upon by the study coordinator and sponsor. Follow up information from these visits will be provided to site, sponsor and to Principal Investigators in a timely manner for their reference purposes.

Protocol

Study Title: Methylation Diet and Lifestyle (MDL) Study

PI: [name], ND, MPH and [name], ND

IRB #: RB100217

Approval Date: 2.9.18

Ver. 1.1

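### Minor: in D.3.1, 48 randomised, 20% attrition and 40 evaluable do not fit together; 20% off 48 leaves about 38, and 48 to 40 is 16.7%

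*Protocol*

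**What the plan says.** Section D.3.1 of the protocol gives the sample size as 48 and explains it in one sentence, which plans to randomise "up to 48 people which will allow for 20% attrition such that we have an evaluated sample size of 40". Section D.1 repeats the total and splits it equally: "We will recruit forty-eight participants with 24 randomized to each study group".

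Three other statements bear on how many men reach the analyses:

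- Section D.6, on a participant who leaves early: if he "withdraws before the second visit, they will be replaced, however participants who withdraw between the second and third visits will not be replaced".
- Section G.4, on the primary mixed model: "any participants who have baseline data only will be excluded from analysis".
- Section G.4, on a follow-up analysis: "we will re-analyze changes from Week 1 to Week 9, using data from completers only".

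The protocol gives no effect size, standard deviation, significance level or power for the 40, so only the attrition arithmetic can be checked.

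**The concern.** The sentence in D.3.1 ties three numbers together, and any two of them contradict the third. The 20% is described as attrition, that is, loss from the men randomised. On that denominator, 48 men do not become 40.

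These are the only figures in the protocol that explain the sample size. A reader cannot tell from them whether the trial planned for 8 losses or for 9 to 10, or whether 40 or about 38 evaluable men were expected.

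The analyses to which an evaluable number matters are those that need Week 9 data. Examples are the completers re-analysis, the MYMOP comparison of "changes over the entire 9-week intervention period", and the CpG comparison where no final saliva sample is obtained after withdrawal. Other Week 9 measures are in the same position.

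**Working it through.** **Inputs.** Randomised N = 48 (D.3.1 and D.1). Attrition d = 20% (D.3.1). Evaluable n = 40 (D.3.1).

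**Reproducing the plan's figure.**

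- Adding 20% to the evaluable number: n x (1 + d) = 40 x 1.20 = 48. This matches exactly.
- Allowing for a 20% loss from those randomised: n / (1 - d) = 40 / 0.80 = 50. This does not match.

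The 48 therefore appears to come from the first formula, while the sentence describes the second.

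**Checking each pair against the third figure.**

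| Keep | Formula | Result | Stated |
|---|---|---|---|
| 48 and 20% | 48 x 0.80 | 38.4 evaluable | 40 |
| 48 and 40 | 1 - 40/48 = 8/48 | 16.7% attrition | 20% |
| 40 and 20% | 40 / 0.80 | 50 randomised | 48 |

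**Whole men.** 20% of 48 is 9.6. Nine losses (9/48 = 18.75%) leave 39, and ten losses (10/48 = 20.8%) leave 38. Neither gives 40.

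**Effect on precision.** With 38 men instead of 40, standard errors grow by a factor of sqrt(40/38) = 1.026, or about 2.6%.

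**Does the replacement rule in D.6 close the gap?** Take 10 losses, of which e occur before Visit 2, and assume that every replacement completes.

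- If 48 is a ceiling that includes replacements, 48 - 10 = 38 men have Week 9 data.
- If replacements come on top of 48, 48 - (10 - e) = 38 + e men have Week 9 data: 38 for e = 0, 40 for e = 2, 43 for e = 5.

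The result reaches 40 only under particular values of e, and the protocol does not link the rule to the 20%. The rule may change how many men are finally available, but it does not make the sentence consistent.

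**Primary mixed model.** Men who leave after Visit 2 still contribute data. Only men with baseline data alone drop out, so without any replacement the model keeps 48 - e men. That falls below 40 only if e is 9 or more. With replacement it stays at 48.

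**The case against.** The strongest defence is that 20% was meant as over-recruitment: 8 extra men on a target of 40 is exactly 20%, and the 48 is used consistently in D.1 and D.3.1. On that reading only the label is loose. It is a plausible account of how the figure arose, but the sentence speaks of attrition, withdrawals and dropouts, which are losses from those randomised, and on that basis the rate is 16.7%.

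A second objection is that nothing depends on the 40: the protocol calls the trial preliminary and gives no power calculation. Misstating an allowance also does not change how many men actually leave. This stands, and it is why the point is minor.

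A third is that 38 is one choice of rounding. Nine losses stay within a 20% allowance and leave 39, so the gap is 1 to 2 men. That is fair, and any restatement should say about 38, or 38 to 39.

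Finally, how replacements are counted and what evaluable means may be settled in a statistical analysis plan that is not at hand. That is accepted, and the finding does not rest on either.

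**Conclusion.** The sentence in D.3.1 is wrong as written. Of 48 randomised, 20% attrition and 40 evaluable, at most two can hold together. The discrepancy is 38 to 39 men against 40, or 16.7% against 20%, or 48 randomised against 50. Rounding does not explain it, and the replacement rule does not resolve it.

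The severity is minor. No loss of power can be claimed, because no power is stated. No shortfall is established for the primary mixed model. The conclusion assumes only that attrition means loss as a share of those randomised, which is how the sentence uses it. The replacement scenarios assume in addition 10 losses and that all replacements finish, but the conclusion does not depend on them.

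**What to change.** Restate the sentence in D.3.1 in one of two ways:

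- 48 randomised allows for 8 losses (16.7%), leaving 40 evaluable; or
- 48 randomised with about 20% attrition leaves about 38 evaluable (38 to 39).

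Either is a change of one sentence with no extra enrolment. The cost is that the stated attrition allowance or the stated evaluable number becomes slightly less favourable. If the sponsor wants to keep both 20% and 40, the consistent number randomised is 50 (25 per group), which means two more men and matching changes in D.1 and D.3.1.

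While the sentence is open, it would help to add whether replacements for men who leave before Visit 2 count within the 48, and whether evaluable means included in the mixed model or having Week 9 data. This is a clarification only; the correction does not depend on it.
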